## **AF Detection Analysis:**

Analysis for the study focus on the performance of daily wear of the Pulsewatch system for 9 hours compared to standard Cardiac Insight patch monitoring over the course of 14 days. We will examine the system's accuracy for pAF identification as well as estimation of AF burden. A participant will be classified as having pAF or not at the end of the 14-day monitoring period based on the gold standard monitor. Data from the Pulsewatch is divided into 30-second segments for analysis and a positive reading will be defined as AF being detected in at least 7 out of 10 continuous data windows (5 minutes). The total number of positive readings collected over 14 days from Pulsewatch will be used as the independent variable in a logistic regression to predict the binary outcome of pAF (yes vs. no). The area under the receiver operating characteristic (ROC) curve (AUC) will be calculated based on the results from the logistic regression to evaluate Pulsewatch performance for pAF screening. From the ROC curve, we can identify the cutoff point of total number of positive readings that produces the highest sensitivity and specificity combination.

Preliminary data suggest that Pulsewatch will have sensitivity, specificity and AUC of at least .9 to detect pAF. Assuming .

Similar analysis will be conducted using the % of positive readings among all readings collected from each participant as the independent variable. The 95% confidence intervals (CI) of the AUC will be calculated using formula given by Hanley and McNeil. We will then conduct exploratory analyses to examine whether characteristics affect watch performance over 14 days. For example, we will compare the area under 2 independent ROC curves of female vs. male participants (or vision impaired vs. not) using a chi-square test. At the end of 14-days we will review the data of 45 participants in Aim 2 intervention and see what % of participants have AF. If we see less than 5% of all participants using the devices have AF, we will have an adaptive protocol for analysis. We would ask participants to extend their use of the devices for an additional 14-days and continue to monitor the participants for potential AF cases. Their follow up assessment for participants in Aim 2 of Part II would be at the end of the 28 days if we take this approach.

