## 4) **Objectives\***

The objectives of this project are to develop a mobile device application with providers and patients that is both usable and accurate. The mobile device application will collect and extract RR interval data and use real-time algorithms for accurate detection of atrial fibrillation (AF) from mobile devices, including a smartwatch. Our central hypothesis is that a wrist-based wearable paired with a smartphone application will detect paroxysmal AF (pAF) with high sensitivity and specificity when compared to conventional cardiac monitors and will be found acceptable by stroke and cardiology patients and their providers. To accomplish this goal, our study will have two phases, a developmental phase and a testing phase. The overall objective will be accomplished by testing our central hypothesis after achieving the following specific aims:

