## 9. Study Timelines\*

The first year to 1.5 years of the study will be focused on achieving Aim I (**Part I – design of the application**). Focus groups will be scheduled on a rolling basis over Year 1 and will be strongly influenced by the coordinator and room availability, as well as participant preference. The Hack-

a-thon will also be scheduled at or around the end of Year 1 of the study (Spring 2019). Participants will be advised of when the event will be held.

Enrollment for Aims 2-3 (**Part II**) will begin in Year 2 and will run for 3 years. At enrollment, participants will be asked to use a cardiac monitor for 14 days and return for a study visit to evaluate device usability and accuracy. Thereafter, we will ask a randomly selected subsample to continue to use the device for an additional 30 days for a total of 44 days. We will hold additional semi-structured exit interviews for select Aim 2 intervention participants who used the Pulsewatch devices for 14 days.

Study Year	1				2				3				4			
Quarter	1	2	3	4	1	2	3	4	1	2	3	4	1	2	3	4
DEVELOPMENT/ENHANCEM	ИE	N٦	(/	۱in	n 1	)										
Formative patient focus groups & provider interviews																
Analysis of formative qualitative data																
"Hack-a-thon" Stakeholder- Agile Team Meeting																
Refine & Integrate AF, skin contact, & MNA algorithms																
EVALUATION/DEPLOYMENT (Aims 2 and 3)																
Smartwatch deployed in stroke population																
Follow-up interviews/exit interview assessment of app																
Data analysis																

The Pulsewatch study will be conducted over a 4-year period; see table below.

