#### PULSEWATCH INVESTIGATOR STUDY PLAN

The PI, Co-Is, 4 participants, 4 provider champions, and computer programmers and engineers from the University of Connecticut (UConn) will meet at the University of Massachusetts Medical School (UMMS) in a conference room to create the final Pulsewatch technology to be deployed in Aims 2 and 3. Modeled on "Hack-a-thons" in the software engineering industry, we will drive innovation by creating team synergy and accelerating product development. This meeting will likely occur in the Albert Sherman Center 7th floor conference room. Patient participants will receive parking vouchers and compensation. Providers will not be compensated. Light refreshments will be provided for all. The meeting will take place over a single day (8-hours) to accommodate the busy schedules of providers and participants. After the Hack-a-thon, the study team will meet to review and encode changes to the application.

The purpose of the Hack-a-thon meeting is to optimize the interactivity and usability of Pulsewatch, guided by information gleaned from focus groups. Using this format, end users (providers and patients) can suggest changes, and programmers will make modifications in realtime. Using a combination of focus groups and agile programming is an innovative as well as sound approach to designing apps. This event will be a critical aspect for Aims 2 and 3 to help develop the interface and management of the app for patients to use. At the Hack-a-thon, participants will be asked to use a prototype of the Pulsewatch app and the system, and then provide feedback on what they think of the system. Programmers will make modifications to the application in real time. While programmers are making those modifications, participants may take a break during the Hack-a-thon, and then come back at a later time during the event to see the final product.

The individuals who will be invited to this Hack-a-thon event will be participants and providers from the focus groups. At the focus groups, we will provide a fact sheet about the day-long Hack-a-thon and a contact sheet for people who may be interested in being invited. We will explain that they may accept or decline the invitation. (Please see Fact Sheet: Patient Hack-a-thon in our eIRB submission). Study staff will follow-up with interested participants and providers by telephone or email. Participants will have the option to opt-out or confirm their attendance at the Hack-a-thon.

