To fine tune and maximize the accuracy of our MNA algorithm, we will use data collected on AF subjects (Aims 2 and 3) using the Pulsewatch system. We will compare the performance of our MNA algorithm using the Pulsewatch signal to the simultaneous gold-standard Cardiac Insight patch. The data analysis and statistical evaluations will be similar to our recently published article on our MNA detection/reconstruction algorithm, but will also involve calculation of absolute error of the estimated heart rate via our algorithm to the reference Holter ECG-derived heart rate. Moreover, we will calculate sensitivity, specificity and accuracy of AF detection using our algorithm when compared to Cardiac Insight patch data.

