Aim 2 Power: Preliminary data suggest that Pulsewatch will have sensitivity, specificity and AUC of at least .9 to detect pAF. We calculate the width of 95% CI for AUC that ranges from .90 to .95 using the proposed sample size of 90 and an estimated rate of 20% patients with pAF. The width of the 95% CI ranges from .14 to .20. The proposed sample size will therefore give a quite precise estimate of Pulsewatch performance relative to the gold standard.

Aim 3 Analysis: The primary analysis focuses on app adherence use in 30 users asked to continue to use the watch and upload readings daily for 1 month. We will determine daily adherence (yes vs. no) based on whether or not daily smartwatch pulse recordings are present. We will examine whether participant characteristics, e.g., sex, cognitive impairment, or a high degree of stroke-related disability (Barthel Index), affect the likelihood of adherence over the 1 month study period. We will use a mixed effects logistic regression model including the participant as the random effect to capture the correlation among repeated measures from the same participant, uses participant characteristics as the fixed effects, and a binary indicator of daily adherence as the dependent variable. We will also examine the adherence time-trend by

including time (day) as a fixed effect in the model and patient as a random effect to estimate the slope of adherence over time. To examine whether the time trend varies by participant characteristics, we will include the interaction between characteristics and time in the model so that the slope of adherence over time can be estimated for each category of patient characteristic variables and be compared among the categories (e.g., pAF diagnosed vs. no pAF). Secondary analyses will examine rates of adherence to Pulsewatch ECG prompts and will compare Pulsewatch users to the usual care group with respect to stroke-related quality of life, anxiety, and self-activation. We will calculate the change score between baseline and 1 month as dependent variable. First, a *t*-test will be used to compare 2 study groups on the change score. A linear regression model, which will include group indicator (Pulsewatch users vs. usual care) as the independent variable and possible confounders (e.g., medication adherence and patient demographics) as covariates, to estimate adjusted group differences on the change scores.

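### The participant-level pAF cut-off is searched for in the same Aim 2 data that would show its accuracy, so sensitivity reported at that cut-off would be optimistic on average

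*Protocol*

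**What the plan says.** The protocol (section 13, AF Detection Analysis) and the SAP (Aim 2 Analysis) describe the same procedure. Each participant is classified as pAF or not from the 14-day reference monitor. The total number of positive Pulsewatch readings enters a logistic regression for pAF, and an ROC curve and AUC are derived from it. Both documents then state: "From the ROC curve, we can identify the cutoff point of total number of positive readings that produces the highest sensitivity and specificity combination". A similar analysis is planned with the percentage of positive readings, which implies a second possible cut-off.

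The rule of 7 out of 10 windows in the protocol defines one positive reading. It does not classify a participant. Neither document states a participant-level cut-off in advance, a hold-out sample, cross-validation, a bootstrap or any other optimism correction. The CI method (Hanley and McNeil) and the stated precision cover the AUC only.

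The central hypothesis in protocol section 4 is that the system "will detect paroxysmal AF (pAF) with high sensitivity and specificity when compared to conventional cardiac monitors". On expected performance, both documents say: "Preliminary data suggest that Pulsewatch will have sensitivity, specificity and AUC of at least .9 to detect pAF". The SAP's precision statement is calculated "using the proposed sample size of 90 and an estimated rate of 20% patients with pAF". Under Smartwatch Data the protocol adds: "Moreover, we will calculate sensitivity, specificity and accuracy of AF detection using our algorithm when compared to Cardiac Insight patch data". It does not say whether this is per segment or per participant, or at what cut-off.

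**The concern.** A cut-off chosen to make sensitivity and specificity jointly as high as possible in one sample fits the chance features of that sample. Reading both measures from the same participants therefore overstates, on average, what that cut-off would achieve in new patients. The excess is larger in the smaller group, here the pAF cases, so it falls mainly on sensitivity.

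Sensitivity and specificity are the quantities named in the central hypothesis, and the searched cut-off is the only participant-level route to them that the documents describe. If the values at that cut-off are offered as evidence for the hypothesis, part of the apparent sensitivity comes from the search and not from the device.

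**Working it through.** **Inputs.** From the SAP (Aim 2 Power): n = 90, pAF rate 20%, AUC .90 to .95, stated CI width .14 to .20. Hence 0.20 × 90 = 18 cases and 72 non-cases. The documents give no distribution for the count of positive readings, so every score shape below is an assumption. So is the figure of 9 cases (10% of 90), used to show the effect of a lower pAF rate.

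**Step 1: the plan's own figure.** Hanley-McNeil, with A = AUC, Q1 = A/(2−A), Q2 = 2A²/(1+A):

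SE² = [A(1−A) + (18−1)(Q1−A²) + (72−1)(Q2−A²)] / (18 × 72)

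- A = .90: Q1 = .8182, Q2 = .8526. The three terms are .0900 + .1391 + 3.0268 = 3.2559. Divided by 1296 this gives SE = .0501, and width = 2 × 1.96 × SE = .196.
- A = .95: Q1 = .9048, Q2 = .9256. The terms are .0475 + .0385 + 1.6430 = 1.7290. SE = .0365, width = .143.

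These match .20 and .14. The AUC uses no cut-off, so the search does not touch it.

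**Step 2: optimism from the search.** In each simulated trial of 90, take the cut-off that maximises sensitivity + specificity. Record the apparent sensitivity there, subtract the true population sensitivity at the same cut-off, and average (8,000 trials per row). Normal scores have equal variance. Counts are negative binomial with extra zeros: case mean 60 to 100, non-case mean 1 to 3, extra zeros 2 to 5% in cases and 50 to 80% in non-cases.

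| Assumed shape | Cases | Sensitivity, apparent / true | Excess, sensitivity | Excess, specificity |
|---|---|---|---|---|
| Normal, AUC .90 | 18 | .862 / .785 | .077 | .019 |
| Normal, AUC .95 | 18 | .913 / .847 | .066 | .015 |
| Counts, AUC .909 | 18 | .821 / .754 | .068 | .011 |
| Counts, AUC .936 | 18 | .879 / .826 | .053 | .005 |
| Counts, AUC .967 | 18 | .922 / .863 | .059 | .006 |
| Normal, AUC .90 | 9 | .889 / .764 | .125 | .014 |
| Normal, AUC .95 | 9 | .935 / .829 | .107 | .010 |
| Counts, AUC .909 | 9 | .848 / .734 | .113 | .005 |

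Differences were taken before rounding. Three further sets of results:

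- Normal scores with AUC about .965, where sensitivity and specificity can both be .9, give an excess of about .06 at 18 cases.
- Six log-normal count shapes with extra zeros (AUC .86 to .93) give .037 to .072 at 18 cases and .072 to .115 at 9.
- With 18 cases, apparent sensitivity exceeds the true value in 65 to 86% of trials, depending on shape. In the rest there is no excess.

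**Step 3: both measures at .9.** With 18 cases this needs at least 17/18 and at least 65/72. For a cut-off fixed at the true optimum under normal scores, sensitivity and specificity both equal Φ(d/2) with d = √2 × Φ⁻¹(AUC). That is .818 (AUC .90) and .878 (AUC .95).

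- AUC .90: P(≥17 of 18) × P(≥65 of 72) = .134 × .036 = .005. With the searched cut-off: about .03.
- AUC .95: .335 × .332 = .11. With the searched cut-off: about .24.

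**Step 4: what correction achieves at 18 cases** (five shapes, 1,000 trials each, 100 bootstraps).

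| Estimate of sensitivity | Mean bias | Root-mean-square error |
|---|---|---|
| Uncorrected | about +.04 to +.08 | .095 to .122 |
| Leave-one-out | −.004 to +.013 | .096 to .129 |
| Bootstrap | +.016 to +.036 | .084 to .111 |

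Leave-one-out removes more of the mean bias but does not lower the overall error. The bootstrap lowers the overall error and leaves a small residual bias. The exact (Clopper-Pearson) 95% CI for 16/18 is .65 to .99.

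**The case against.** The strongest reply is that the harm is conditional. The documents say only that the cut-off can be identified. The SAP's table of quantitative analyses lists the AUC as the product of this analysis, and CI and precision are given for the AUC alone. No sentence says that sensitivity at the searched cut-off will be a reported result. This stands, and it is why the point is worded as conditional. It does not remove the point: the AUC by itself does not show the sensitivity and specificity named in the hypothesis.

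A reader might infer that the search inflates the chance of meeting a .9 target. The documents do not support that. The .9 is a planning expectation drawn from preliminary data, with no test or decision attached. Counting sensitivity alone would also exaggerate the contrast, because the expectation covers both measures. The comparison in step 3 uses an optimal cut-off that nobody can know in advance. At AUC .90 a cut-off fixed half a standard deviation lower has true sensitivity Φ(.906 + .5) = .92, and so reaches 17/18 with probability .57, at the price of specificity .66.

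It is also fair to say that .04 to .08 is small beside an interval of .65 to .99. That limits the importance of the point. But the interval does not show a bias in a known average direction, and the correction costs little.

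**Conclusion.** The point holds in a limited form. Sensitivity taken at the searched cut-off would be optimistic on average: by about .04 to .08 with the planned 18 cases (.06 to .08 for normal scores with AUC .90 to .965), and by about .07 to .13 with 9 cases. Specificity would be optimistic by at most about .02. The direction for sensitivity was the same in every shape tried. The size rests on assumed score distributions, and any one study may show no excess. The AUC and its stated precision are sound.

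A reader might also infer that the whole Aim 2 evaluation is tuned on its own test data. Protocol section 13 does plan to fine-tune the motion/noise-artifact algorithm on Aim 2 and 3 participants, while section 11 describes the Hack-a-thon as the meeting "to create the final Pulsewatch technology to be deployed in Aims 2 and 3". The documents do not say which algorithm version produces the Aim 2 results, so that inference is not established. It is a separate clarification to request and forms no part of the sizes given here.

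**What to change.** In the SAP (Aim 2 Analysis) and protocol section 13:

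- Keep the AUC analysis as planned.
- Name in advance which predictor, the number or the percentage of positive readings, is primary for the cut-off.
- Label sensitivity and specificity at the searched cut-off exploratory.
- Report both measures with a bootstrap optimism correction that resamples participants and repeats the cut-off search in each resample. In each resample, take the sensitivity at its own best cut-off and subtract the sensitivity of that cut-off in the full data. Subtract the mean of these differences from the apparent value, treat specificity the same way, and give a CI. The bootstrap is preferred to leave-one-out for its lower overall error at 18 cases.
- Alternative: if a cut-off can be justified from data outside Aim 2, fix it before the patch results are merged and give exact CIs. The documents themselves supply no such value.

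The cost is a few lines of text and one short computation, with no extra participants. Reported sensitivity will be somewhat less favourable. It will also remain imprecise, because correction reduces the bias but cannot make up for having about 18 cases.

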# **Usability Analysis:**

We also aim to examine whether participant characteristics (e.g., demographics, level of technology use, cognitive impairment, etc.) affect usability and adherence of the Pulsewatch system. Usability will be examined by semi-structured interviews, investigator generated

questions regarding user experience, and the System Usability Scale (SUS), a validated instrument for perceived system usability. Investigator generated questions will have responses in a 5-point Likert-like scale, and ordinal regression will be used to evaluate participant characteristics that may be associated with more favorable responses regarding usability of the Pulsewatch system. The SUS score ranges between 10 and 100, and linear regression will be used to examine the participant level factors that are associated with higher SUS scores. Logistic regression will also be used to examine whether certain participant factors are associated with having a SUS score of over 68, the acceptable cut off being deemed as a highly usable system.

## Adherence Analysis:

In Aim 3 of Part II of the study, adherence will be operationalized to determine whether pulse recordings were present on each day over the 30-day period. We will examine whether participant characteristics, e.g., sex, cognitive impairment, or stroke-related quality of life, affect the likelihood of adherence over the 1-month study period. We will use a mixed effects logistic regression model, including the participant as the random effect to capture the correlation among repeated measures from the same participant, using participant characteristics as the fixed effects, and a binary indicator of daily adherence as the dependent variable. We will also examine the adherence time-trend by including time (day) as a fixed effect in the model and participant as a random effect to estimate the slope of adherence over time. To examine whether the time trend varies by participant characteristics, we will include the interaction between characteristics and time in the model so that the slope of adherence over time can be estimated for each category of participant characteristic variables and be compared among the categories (e.g., pAF diagnosed vs. no pAF). Secondary analyses will examine rates of adherence to Pulsewatch ECG prompts and will compare Pulsewatch users to the usual care group with respect to stroke-related quality of life, anxiety, and self-activation. We will calculate the change score between baseline and 1 month as a dependent variable. First, a t-test will be used to compare 2 study groups on the change score. We will use a linear regression model, which will include group indicator (Pulsewatch users vs. usual care) as the independent variable and possible confounders (e.g., medication adherence and participant demographics) as covariates, to estimate adjusted group differences on the change scores.

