Statistical Plan

Smartwatch Monitoring for Atrial Fibrillation After Stroke

NCT #: NCT03761394

Date of document: 11/20/18

Pulsewatch Statistical Plan:

Pulsewatch usability assessment via qualitative interviews and focus groups: Interviews will seek individual opinions about the usability and acceptability of Pulsewatch and will ask about: 1) ways in which Pulsewatch was intrusive; 2) how using Pulsewatch caused fatigue; 3) ways in which participants thought Pulsewatch use promoted health; 4) reflections on the trustworthiness of Pulsewatch (e.g., ‘belief’ of findings); and 5) participant comfort using Pulsewatch to communicate with their clinician. We anticipate that these 5 areas are highly individual and vary from person-to-person. Therefore, qualitative interviews, rather than standardized questionnaires, are needed since they provide an opportunity for users to describe their personal experiences in detail. In addition, we will ask participants to identify the amount of time they spent using Pulsewatch during a typical day. To assess another measure of participant’s acceptance, we will ask the participant to gauge their interest in continuing to use Pulsewatch even though their participation in the study has concluded. Participants who ceased using Pulsewatch will be identified and contacted by the staff for semi-structured interviews to understand why they stopped. We will conduct 2-4 focus groups (12-16 users total) to generate data on barriers to, and facilitators of, Pulsewatch use. In distinction to Aim 1 focus groups, which focus on learning what capabilities users want, Aim 3 focus groups center on ‘what worked’ and ‘what didn’t’ and whether or not long-term use introduces or reduces stress. We will also solicit feedback on the Interactivity Manager and Annotation Panels, features developed too late in Aim 1 to be fully explored by Aim 1 focus groups. Groups will be stratified by Pulsewatch adherence during the intervention period (<50%, 50-74%, >75%). We anticipate that with 4 focus groups we will reach saturation. However, if this is not the case, we will conduct 2 additional groups (n=12). Semi-structured and open-ended agendas will be written and IRB submitted. Discussions will be audio-recorded, transcribed and de-identified, protecting confidentiality by replacing names with study IDs.

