Aim 3 Power: For the primary analysis, a power analysis was conducted comparing the time-averaged probability of adherence between 2 groups using a repeated measures regression model. We used 12 and 18 patients (total=30) in each of the groups (e.g., cognitively impaired vs. not), and type I error=5%. With 30 adherence measures for each patient and the probability of adherence in 1 group (e.g., cognitively impaired) = 50%, we will have 80% power to detect a difference in the adherence of 12%-16% in the other group when auto-correlation ranges from .2-.5). The difference in the probability of adherence decreases to 9%-12% when the probability in 1 group=80%. Therefore, our proposed n=30 for Pulsewatch users provides sufficient power to detect differences in the probability of adherence of 9%-16% between 2 groups (e.g., cognitively impaired vs. not). The secondary analysis power calculation was conducted comparing 30 users to 30 controls on continuous outcomes (e.g., anxiety) using a *t*-test. We will have a power of 80% to detect an effect size of .74 with 5% type I error.

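### The Aim 3 adherence-trend tests make no allowance for serial correlation between days; if the SAP's .2-.5 correlation is all serial, they reject falsely about 9-12% to 21-26% of the time instead of 5%

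*Protocol*

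**What the plan says.** The Protocol, section 13 (Adherence Analysis), fits a mixed effects logistic model to a daily yes/no adherence indicator over 30 days, "including the participant as the random effect to capture the correlation among repeated measures from the same participant". The trend comes from "including time (day) as a fixed effect in the model and participant as a random effect to estimate the slope of adherence over time". To see whether the trend differs by characteristic, "we will include the interaction between characteristics and time in the model".

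The SAP (Aim 3 Analysis) says the same: "We will use a mixed effects logistic regression model including the participant as the random effect", with the trend obtained by "including time (day) as a fixed effect in the model and patient as a random effect". Neither document names a random slope for day, a serial correlation structure or robust standard errors.

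The SAP's Aim 3 Power paragraph sizes a different contrast, the time-averaged probability of adherence in 12 versus 18 users with 30 daily measures each. It gives detectable differences of 12%-16% (50% adherence in one group) and 9%-12% (80%) "when auto-correlation ranges from .2-.5". The SAP's opening section on usability adds: "Participants who ceased using Pulsewatch will be identified and contacted by the staff".

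**The concern.** With a participant random intercept alone, the model assumes that days are independent once a person's overall level is known, and that everyone in a category shares one slope. A random intercept absorbs stable differences between people. It does not absorb runs of good and bad days, or a person who stops. Such runs look like slopes within a person, so the model's standard error for the slope is too small.

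The power paragraph appears to assume exactly this kind of day-to-day dependence, while the analysis model has no term for it. At stake are the confidence interval for the overall slope and the tests of which characteristics change it. A characteristic with no effect would be declared to change the trend more often than 5% of the time. Several example characteristics are named (sex, cognitive impairment, disability or quality of life, pAF status), and no multiplicity control is stated.

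**Working it through.** **Inputs.** From SAP Aim 3 Power: 30 daily binary measures, 12 versus 18 users, correlation ρ = .2 to .5, adherence .5 or .8, type I error 5% (two-sided assumed), power 80%. From Protocol section 11: 60 Aim 3 users, simulated as 24 versus 36 because the SAP has 30.

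**Step 1: reproduce the SAP's detectable differences.** Effective sample size per group = users × 30 / DE. The detectable difference d solves d = (1.960 + 0.842) × √[p₁(1−p₁)/n₁ + p₂(1−p₂)/n₂], with p₂ = p₁ + d and the 12-user group at p₁.

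- Serial AR(1): DE = 1 + 2Σ(1 − k/30)ρᵏ for k = 1 to 29, which is 1.48 at .2 and 2.87 at .5. So n₁ = 360/1.48 = 243 and n₂ = 540/1.48 = 365 at .2; n₁ = 126 and n₂ = 188 at .5.
- Exchangeable: DE = 1 + 29ρ, which is 6.8 and 15.5.

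| Adherence in one group | SAP | Serial | Exchangeable |
|---|---|---|---|
| 50% | 12%-16% | 11.5%-15.8% | 24%-34% |
| 80% | 9%-12% | 8.6%-11.5% | about 16%-20% |

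The serial figures round to the SAP's. The exchangeable ones are nowhere near. The SAP's correlation is therefore taken as serial, by inference.

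**Step 2: expected effect on the slope test.** Let t be the centred day and R the matrix with entries ρ^|j−k|. The true variance of a within-person slope, relative to the variance under independent days, is V = t′Rt / t′t. This is 1.44 at .2 and 2.60 at .5. Scaling by the within-person residual variance instead gives 1.46 and 2.78. A nominal 5% test then has error 2Φ(−1.96/√V):

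- ρ = .2: 1.96/√1.44 to 1.96/√1.46, about 10%
- ρ = .5: 1.96/√2.60 to 1.96/√2.78, about 22%-24%

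**Step 3: simulation.** Null data with no trend and no group effect, random-intercept logistic model by maximum likelihood, Wald tests, 1,500 runs per cell (simulation error about ±1.1 points at 5%), adherence .5 and .8:

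| Correlation | Users | Day slope | Characteristic × day |
|---|---|---|---|
| Serial .2 | 30 | 9.5%-10.5% | 9.9%-10.5% |
| Serial .2 | 60 | 9.5%-10.5% | 9.1%-11.5% |
| Serial .5 | 30 | 23.9%-24.5% | 24.1% |
| Serial .5 | 60 | 24.8%-25.3% | 22.5%-23.7% |
| Exchangeable .2 or .5 | 30 or 60 | 3.9%-6.0% | 3.9%-6.0% |

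Separately coded simulations (300 to 1,000 runs per cell) widen these ranges only to about 9-12% at .2 and 21-26% at .5. The exchangeable rows show that the inflation comes from serial dependence and not from the fitting. Doubling the number of users does not remove it.

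**Step 4: part of the correlation from stable participant differences.** Total lag-1 correlation is held at .2 or .5 (12 versus 18, about 600 runs per cell, error 2-3 points). The split is assumed, since the documents give none.

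| Share from participants | Interaction error at .2 | At .5 |
|---|---|---|
| Half | 6.5%-6.8% | 13%-16% |
| 80% | 5.5%-7.1% | 8.3%-9.1% |

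**Step 5: permanent stopping.** With 10%, 20% or 30% of users assumed to stop for good, equally in both groups, interaction error was 22%-24%, 30%-32% and 34%-37% in one set of runs, and 14%, 21% and 27% in another. The gap reflects assumptions about baseline adherence, heterogeneity and stopping times, none of which the documents give.

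**Step 6: level comparison and remedy.** The time-averaged comparison between groups stayed at about 4%-7% under serial correlation. A logistic GEE with participant-clustered standard errors, a small-sample factor and a t reference on participants minus 2 gave 3.0%-6.3% for the interaction in every cell, including those with stopping, and 4.0%-6.3% for the slope under serial correlation.

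**The case against.** Four points can be made for the plan.

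First, the participant effect is there to absorb correlation within a person. If much of the correlation is stable differences between people, the inflation is modest, as step 4 shows. This stands: 9-26% is the range when all the correlation is serial, not an unconditional property of the plan. A reader might infer that the SAP itself commits to that case. It does not, since it never writes AR(1) or lag-1, and its correlation is stated for the time-averaged contrast. What remains is that its power figures fit serial correlation and not the exchangeable alternative, and that at .5 the error is still 13%-16% when half is serial.

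Second, no text says that the intercept is the only random effect. A random slope is not excluded, although it would normally be named if intended.

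Third, a reader might infer that the SAP expects permanent stopping at a material rate. It only says that those who stopped will be contacted for interview; it gives no rate or pattern. The 14%-37% range is illustrative.

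Fourth, the trend tests are introduced as additional examinations. The SAP's Table 2 lists daily use against characteristics with no day interaction, and only the time-averaged contrast is powered. This stands, and it limits the severity.

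**Conclusion.** The point holds in conditional form. As ordinarily read, the planned model gives slope and slope-by-characteristic tests with no allowance for serial dependence. If the SAP's .2-.5 correlation is wholly serial, false rejection is about 9-12% at .2 and 21-26% at .5. It is lower with a mixture and about 5% if the correlation is purely exchangeable. But in that last case the SAP's detectable differences would be too small, so the analysis and power sections need to be reconciled either way.

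The conclusion rests on two inferences (random intercept only; AR(1)-type correlation) and on two-sided testing. Permanent stopping would add inflation of unknown size.

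It would be tempting to conclude that the Aim 3 adherence analysis as a whole is unsound. The documents do not support that: the powered time-averaged comparison keeps close to its nominal error, and the affected tests are follow-on analyses within the adherence section. Severity is moderate.

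**What to change.** In Protocol section 13 (Adherence Analysis) and SAP Aim 3 Analysis, state the random-effects structure. Base the day slope and every characteristic-by-day test on participant-clustered robust standard errors, with a small-sample correction and a t reference on participants minus 2. A logistic GEE is one way and is the version checked above. The random-intercept model can stay for the level comparison. In SAP Aim 3 Power, state which correlation structure the .2-.5 refers to.

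The cost is a short text change and wider trend intervals. With GEE, the trend also becomes population-averaged while the level comparison from the mixed model stays participant-specific, and the SAP should say so. Clustered standard errors on the existing mixed model, or a random slope for day, would change the plan less, but no error rates were obtained for either here.
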